### 4.1. Inclusion Criteriaa

Each potential subject must satisfy all of the following criteria to be enrolled in the study unless otherwise specified:

- 1. Subject must be a man or woman between 18 and 64 years of age, inclusive.
- 2. Subjects must have a primary DSM-5 diagnosis of SAD except those with performance only as a specifier. Subjects with a diagnosis of comorbid Generalized Anxiety Disorder (GAD) or Major Depressive Disorder (MDD) may be included if the investigator considers SAD to be the predominant diagnosis. Subjects with current or lifetime history of ADHD and specific phobia may be included as well.
- 3. Subjects must have a Liebowitz Social Anxiety Scale score  $\geq$  70 at screening and baseline.
- 4. Subjects with a current episode of MDD must have a HDRS17 total score  $\leq 18$
- 5. Subjects must have a body mass index (BMI=weight/height) between 18 and 35 kg/m^2, inclusive, at screening.
- 6. Criterion modified by Amendment 3.
  - 6.1. Before randomization, a **woman** must be either:
  - Not of childbearing potential: postmenopausal (>45 years of age with amenorrhea for at least 12 months, or any age with amenorrhea for at least 6 months and a serum follicle stimulating hormone (FSH) level >40 IU/L); permanently sterilized (e.g., tubal occlusion, hysterectomy, bilateral salpingectomy); or otherwise be incapable of pregnancy
  - Of childbearing potential and practicing a highly effective method of birth control consistent with local regulations regarding the use of birth control methods for subjects participating in clinical studies (i.e. one that results in a less than 1% per year failure rate when used consistently and correctly). This may include:
    - Established and ongoing use of oral hormonal methods of contraception in combination with barrier methods.
    - Established and ongoing use of patch, injected or implanted hormonal methods of contraception.
    - Placement of an IUD or IUS.

Accepted barrier methods as indicated above include:

<sup>a This section has been amended per Amendments INT-1 and 3.

- condom with spermicidal foam/gel/film/cream/suppository
- occlusive cap (diaphragm or cervical/vault caps) with spermicidal foam/gel/film/cream/suppository

Note that a barrier method on its own is not sufficient.

- Male partner sterilization (the vasectomized partner should be the sole partner for that subject).
- True abstinence (when this is in line with the preferred and usual lifestyle of the subject).

Women must agree to continue using these methods of contraception throughout the study and for at least 3 months after receiving the last dose of study medication.

Note: If a woman of childbearing potential who is not heterosexually active becomes active after the start of the study, she must begin a highly effective method of birth control, as described above.

- All women must have a negative pregnancy test at screening and a negative urine pregnancy test on study day 1.
- All women must agree not to donate eggs (ova, oocytes) for the purposes of assisted reproduction during the study and for at least 3 months after receiving the last dose of study drug.
- 7. Criterion modified by Amendment 3.
  - 7.1 **Men** who are sexually active with a woman of childbearing potential and have not had a vasectomy must agree to use a barrier method of birth control e.g., either condom or partner with occlusive cap (diaphragm or cervical/vault caps) with spermicidal foam/gel/film/cream/suppository for the duration of the study plus 3 months after receiving the last dose of study drug, and all men must not donate sperm during the study and for 3 months after receiving the last dose of study drug. In addition, their female partners should also use an additional method of birth control (which may include a hormonal method, an intrauterine device [IUD] or an intrauterine system [IUS]) for at least the same duration.
- 8. Subjects must be otherwise healthy for their age group or medically stable with or without medication on the basis of physical examination, medical history, vital signs, and 12-lead ECG performed at screening or at baseline. If there are abnormalities, they must be consistent with the underlying illness in the study population and not a potential cause of cognitive impairment, with written concurrence with the sponsor's medical monitor.
- 9. Subjects must be otherwise healthy or medically stable on the basis of clinical laboratory tests performed at screening. If the results of the serum chemistry panel [including liver enzymes, other specific tests], hematology, or urinalysis are outside the normal reference ranges, the subject may be included only if the investigator judges the

abnormalities or deviations from normal to be not clinically significant. This determination must be recorded in the subject's source documents and initialed by the investigator.

- 10. Subject must be willing and able to adhere to the prohibitions and restrictions specified in this protocol.
- 11. Subject must be willing and able to fill out self-administered questionnaires.
- 12. Subject must be able to be compliant with self-administration of medication.
- 13. Subject must be able to swallow the study medication whole with aid of water.
- 14. Subject must sign an informed consent document indicating that they understand the purpose of and procedures required for the study and are willing to participate in the study.

## 4.2. Exclusion Criteriaa

Any potential subject who meets any of the following criteria will be excluded from participating in the study unless otherwise specified:

- 1. Subjects who have performance only SAD are excluded. Subjects with other current significant psychiatric condition(s) (Axis 1 under DSM-IV), including, but not limited to, MDD with psychotic features (lifetime), bipolar disorder (including lifetime diagnosis), obsessive-compulsive disorder, borderline personality disorder, eating disorder (e.g., bulimia, anorexia nervosa), autism spectrum disorders, post-traumatic stress disorder (PTSD) or schizophrenia are excluded. Subjects with a diagnosis of comorbid GAD or MDD may be included.
- 2. Subject is currently receiving specific psychotherapy for SAD.
- 3. Has a history of more than two unsuccessful adequate pharmacological treatment trials for SAD, defined as lack of response to at least 10 weeks of treatment at adequate doses (e.g., paroxetine  $\geq$  40 mg/day or its equivalent; or clonazepam  $\geq$  2.5 mg/day or its equivalent).
- 4. Concurrent use of psychotropic medications. Benzodiazepine must be discontinued at least 7 days before screening and antidepressant therapy must be discontinued at least 2 weeks before screening (5 weeks for fluoxetine). Subjects who have had an adequate response to pharmacotherapy should not have this treatment discontinued solely for participation in the study. Subjects who have elected, in consultation with their health care provider, to discontinue pharmacotherapy because of difficulty tolerating the

<sup>a This section has been amended per Amendments INT-2 and 3.

medication may be eligible provided those treatments are stopped according to the guidelines above.

- 5. Subject has a history of or current thyroid disease, thyroid dysfunction and is currently untreated for it. Subjects treated for thyroid disease may be enrolled following review of their records of diagnosis and treatment history by the investigator and with written concurrence with the sponsor's medical monitor to ensure disease/treatment stability and compliance.
- 6. Criterion modified by Amendment 2.
  - 6.1.Subject has clinically significant abnormal findings on physical examination, neurological examination or clinically significant abnormal vital signs indicative of untreated illness (such as infection or hypertension).
- 7. Subject has a clinically significant abnormal finding on 12-lead ECG such as QTc >450 msec for males and females, Left Bundle Branch Block, AV Block second degree or higher, permanent pacemaker or implantable cardioverter defibrillator (ICD) at screening or baseline (Day 1 predose), or any finding which in the opinion of the investigator is not appropriate and reasonable for the population under study. ECG recordings and vital signs may be repeated once and for questions on findings on the ECG a local cardiologist should be consulted.
- 8. Subject has a history of or current liver or renal insufficiency; clinically significant cardiac, vascular, pulmonary, gastrointestinal, endocrine, hematologic, rheumatologic, psychiatric, or metabolic disturbances (e.g. unstable situation needing monitoring or regular dose adaptations). Subjects with liver function analytes higher than the upper limit of normal at baseline should be reviewed with the sponsor. If the subject has any liver function tests >2 times the upper limit of normal, he/she should not be enrolled.
- 9. Subject has a history of malignancy within 5 years before screening (exceptions are squamous and basal cell carcinomas of the skin and carcinoma in situ of the cervix, or malignancy that in the opinion of the investigator, with written concurrence with the sponsor's medical monitor, is considered cured with minimal risk of recurrence).
- 10. If a subject is using a drug with moderate/strong CYP3A4 inhibiting properties at, or prior to, Screening it must be discontinued at least within 1 month prior to Day 1. Note: an existing medication should not be stopped solely for the purpose of the subject entering the study. Moderate and strong inducers of CYP3A4 are prohibited during the study (See Attachment 13).
- 11. Subject has a history of positive tests for hepatitis B surface antigen (HBsAg) or hepatitis C antibody (anti-HCV) positive, or other clinically active liver disease, or tests positive for HBsAg or anti-HCV at Screening.

- 12. Subject tests positive for human immunodeficiency virus (HIV) or antibodies at Screening and is not being treated. Subjects with known HIV infection who are being treated, have shown a good response, are otherwise clinically stable, and can continue to comply with treatment may be enrolled. Subjects requiring treatment with medications that are moderate or strong CYP3A inhibitors (such as most protease inhibitors: see Attachment 13) must be excluded.
- 13. Subject has a history of drug or alcohol use disorder according to Diagnostic and Statistical Manual of Mental Disorders (5th edition) (DSM-5) criteria within 6 months before screening, or positive test result(s) for drugs of abuse (including barbiturates, opiates, cocaine, cannabinoids, amphetamines) at screening. A positive screen for benzodiazepines is allowed if related to recent treatment.
- 14. Subject has taken any disallowed therapies as noted in Section 8, Concomitant Therapy before the planned first dose of study drug.
- 15. Subject has known allergies, hypersensitivity, or intolerance to JNJ-42165279 or its excipients (refer to Investigator's Brochure).
- 16. Subject has received an investigational drug or used an investigational medical device within 3 months before the planned start of study or is currently enrolled in an investigational study.
- 17. Subject is a woman who is pregnant, or breast-feeding, or planning to become pregnant or is a man who plans to father a child, while enrolled in this study or within 3 months after the last dose of study.
- 18. Subject has any condition for which, in the opinion of the investigator, participation would not be in the best interest of the subject (e.g., compromise the well-being) or that could prevent, limit, or confound the protocol-specified assessments.
- 19. Subject has had major surgery, (e.g. requiring general anesthesia) within 8 weeks before screening, or will not have fully recovered from surgery, or has surgery planned during the time the subject is expected to participate in the study or within 4 weeks after the last dose of study drug administration.

*Note: subjects with planned surgical procedures to be conducted under local anesthesia may participate.* 

- 20. Subject has a history of spontaneous, prolonged or severe bleeding.
- 21. Subject has donated one or more units (approximately 450 mL) of blood or had acute loss of an equivalent amount of blood within 90 days prior to study drug administration.
- 22. Subject has a current or recent history of clinically significant suicidal ideation within the past 6 months, corresponding to a score of 4 (active suicidal ideation with some

intent to act, without specific plan) or 5 (active suicidal ideation with specific plan and intent) for ideation on the Columbia Suicide Severity Rating Scale (C-SSRS), or a history of suicidal behavior within the past year, as validated by the C-SSRS at screening or Day 1. Subjects with a prior suicide attempt, or prior serious suicidal ideation/plan  $\geq$  6 months ago, should be carefully screened for current suicidal ideation and only included at the discretion of the investigator.

- 23. Subject is an employee of the investigator or study site, with direct involvement in the proposed study or other studies under the direction of that investigator or study site, as well as family members of the employees or the investigator.
- 24. Subject is unable to comply with the study-specific requirements.

### 4.3. Prohibitions and Restrictionsa

Potential subjects must be willing and able to adhere to the following prohibitions and restrictions during the course of the study to be eligible for participation:

- 1. If a man that is sexually active with a woman of childbearing potential, he must agree to use a double barrier method of birth control and to not donate sperm during the study and for 3 months after receiving the last dose of study drug.
- 2. Subjects must abstain from using illegal drugs (including cannabis and marihuana) from Screening through the end of the post-treatment phase. While cannabis and marihuana use may be sanctioned in some regions, use of cannabanoids during this trial would prevent detection of an effect of JNJ-42165279 and therefore must not be used while participating in the trial. If the subject has a positive urine drug screen during the study, he/she will be discontinued from the study.
- 3. Subjects are prohibited from taking/consuming grapefruit, grapefruit juice, Seville oranges or poppy seeds from Screening through the end of the post-treatment phase.
- 4. For a list of prohibited medications, please see Section 8 (Prestudy and Concomitant Therapy).
- 5. The use of limited amounts of alcohol (up to 2 drinks daily) will be allowed.
- 6. Subjects are not allowed to participate in cognitive behavioral therapy for SAD during their participation in the trial.

<sup>a This section has been amended per Amendment INT-1.

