## 8. PRESTUDY AND CONCOMITANT THERAPYa

Prestudy therapies administered up to 30 days before screening must be recorded at screening.

Concomitant therapies must be recorded throughout the study beginning with signing of the initial informed consent until the end-of-study visit (Follow-up visit). Concomitant therapies should also be recorded beyond this time only in conjunction with new or worsening adverse events until resolution of the event.

All therapies (prescription or over-the-counter medications, including vaccines, vitamins, herbal supplements; non-pharmacologic therapies such as electrical stimulation, acupuncture, special diets, exercise regimens) different from the study drug must be recorded in the CRF. Modification of an effective pre-existing therapy should not be made for the explicit purpose of entering a subject into the study.

The sponsor must be notified in advance (or as soon as possible thereafter) of any instances in which prohibited therapies are administered.

Subjects are not allowed to participate in cognitive behavioral therapy for SAD while participating in this study. Investigators will inform subjects at their baseline visit and remind them at each subsequent visit of the need to enter socially feared situations in order to be able to determine how effective the medication is. At each visit (after the first visit), investigators will ask the subject about social situations that s/he has encountered since the last visit, and how s/he felt in those situations.

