### Prohibited Medications

Refer to Section 4.2 (Exclusion Criteria) for prohibited medications evaluated at Screening.

Subjects must agree not to use any of the following medications with psychotropic properties during study participation, including but not limited to:

• Psychiatric medications, including mood stabilizers, antipsychotics, antidepressants (e.g., MAOIs, SSRIs, SNRIs, or TCAs), or medications to treat anxiety (including benzodiazepines: see below)

<sup>a This section has been amended per Amendment INT-3.

- Sleep medications/medications to treat anxiety:
  - Benzodiazepines: Because concomitant use of benzodiazepines will confound the ability to interpret any potential anxiolytic efficacy signal, sleep aids and anxiolytics from the benzodiazepine class (e.g., lorazepam, temazepam, oxazepam, flurazepam, triazolam etc.) are prohibited from within 7 days prior to Screening and throughout the study duration.

Note: Nonbenzodiazepines sleep aids (including: zolpidem, zaleplon and eszopiclone) are allowed on a PRN (as needed) basis during the study.

- Other Prohibited Medications include:
  - Sedating antihistamines
  - S-adenosyl methionine (SAMe), St. John's wort, ephedra or kava kava
  - Melatonin and ramelteon
  - Opiates, including morphine, codeine hydrocodone, oxycodone, and methadone
  - Anticonvulsants
  - Moderate and strong CYP3A4 inhibitors or inducers (Attachment 13)

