### 9.1.3. Double-Blind Treatment Phasea

#### Day 1

Subjects who successfully complete the screening examination will visit the clinical site on Day 1 during the morning hours.

Prior to dosing the following (baseline) assessments will be performed:

- Body weight
- 12-lead ECG recording (triplicate)

<sup>a This section has been amended per Amendments INT-1, 2 and 3.

- Body temperature
- Supine and standing vital signs (systolic and diastolic blood pressure and pulse)
- C-SSRS
- Clinical safety laboratory assessments under fasted conditions, when feasible (including hematology, serum chemistry, coagulation and urinalysis)
- Blood sample collection for pharmacogenomics
- Blood sample collection for FAAs
- Urine drug screen
- Alcohol screen (in blood)
- All women: Urine pregnancy test
- Review of inclusion and exclusion criteria
- Randomization
- Dispense JNJ-42165279/placebo
- LSAS
- HDRS17 using the SIGH-D
- SIGH-A
- SDS
- GAD-7
- SHAPS
- MOS Sleep-R
- Q-LES-Q
- Behavioral guidance from the investigator
- Record adverse events and concomitant medication

Study medication will be dispensed (incl. drug accountability) and administered as outlined in Section 6, Dosage and Administration. Subjects will self-administer their study medication q.d. as instructed.

On Day 1 dosing will not be time limited and will be performed following completion of the baseline (predose) assessments, which will be witnessed by designated study-site personnel at the study sites.

During the double-blind treatment period, following Day 1, subjects will return to the investigational site at regular time points as indicated in the Time and Events Schedule and further described below.

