2.5.3. Intent-to-Treat (ITT) Analysis Set

The ITT analysis set is defined as all randomized subjects who received at least one dose of study medication (either placebo or JNJ-42165279), and have at least one assessment in the double-blind treatment phase on any of the efficacy parameters. Subjects who withdrew early from the study at the time of study suspension will not be included in the ITT analysis set (7 placebo subjects, 8 JNJ-42165279 subjects). Subjects who had already completed the study at the time it was suspended, however, will be included in the ITT set (9 placebo subjects, 9 JNJ-42165279 subjects).

The ITT analysis set is the analysis set for the efficacy analyses.

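### Psychotherapy for SAD is barred broadly at entry but only as cognitive behavioral therapy on study, so another SAD-directed psychotherapy could start after Day 1 without breaking a rule

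*Protocol*

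**What the plan says.** **At entry.** Protocol Section 4.2, criterion 2, excludes a subject if: "Subject is currently receiving specific psychotherapy for SAD". The term is not defined and is not restricted to one modality. Eligibility is checked again before the first dose; the Day 1 list in Section 9.1.3 includes "Review of inclusion and exclusion criteria".

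**During the study.** Section 4.3, item 6, states: "Subjects are not allowed to participate in cognitive behavioral therapy for SAD during their participation in the trial". Section 8 states the same restriction: "Subjects are not allowed to participate in cognitive behavioral therapy for SAD while participating in this study". Neither mentions any other psychotherapy.

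**Neighbouring rules.**
- Section 8 requires non-drug treatments to be documented: "non-pharmacologic therapies such as electrical stimulation, acupuncture, special diets, exercise regimens) different from the study drug must be recorded in the CRF". This is a recording rule, not a prohibition.
- Section 4.2, criterion 14, is tied to the period before dosing: "Subject has taken any disallowed therapies as noted in Section 8, Concomitant Therapy before the planned first dose of study drug".
- The Section 8 prohibited list covers drugs: "Subjects must agree not to use any of the following medications with psychotropic properties during study participation".

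**Analysis.** SAP Section 2.5.3 states: "The ITT analysis set is the analysis set for the efficacy analyses". SAP Section 4.6 tabulates medications only. SAP Section 4.5 lists deviations by treatment group and has major ones grouped before unblinding.

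**The concern.** The entry rule is broader than the rule that applies once treatment starts, and the protocol gives no reason for the difference. A subject could begin a SAD-directed psychotherapy other than cognitive behavioral therapy during the 12 weeks and stay fully compliant.

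Such therapy could lower the LSAS total score, which is the primary endpoint. Because it starts after randomisation, it does not invalidate the ITT comparison. It can, however, change what the comparison measures if uptake differs by arm. More uptake on placebo pulls the drug–placebo difference toward zero and costs power. More uptake on active pushes the difference away from zero and raises the chance of a positive result for a drug with no effect. Since no rule is broken, the deviation listing would not show it.

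**Working it through.** **1. Does any rule close the gap?**

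| Rule | Covers a non-CBT, SAD-directed psychotherapy started after Day 1? |
|---|---|
| Protocol 4.2, criterion 2 | No; entry only, rechecked on Day 1 |
| Protocol 4.2, criterion 14 | No; before first dose only |
| Protocol 4.2, criterion 18 | No; applies at entry |
| Protocol 4.3, item 6, and Section 8 | No; name cognitive behavioral therapy only |
| Protocol 8, prohibited list | No; medications only |
| Protocol 8, recording rule | Recorded, not barred |
| SAP 4.6 | No; medications only |

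The gap is confined to new starts after Day 1.

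**2. The plan's own sample size.** Inputs from Protocol Section 11.2: difference 10, SD 24, 1-sided alpha 0.20, power 90%, 53 per group. The normal approximation gives 52 per group. A two-sample t-test with 53 per group has power 90.3%, so the stated figure reproduces.

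SE of the difference = 24 × √(2/53) = 4.66 LSAS points.

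**3. Size of a possible shift.** The documents give neither uptake nor benefit. I assume excess uptake *p* of 2% or 5% in one arm (0.02 × 53 = 1.1 and 0.05 × 53 = 2.7 subjects) and a gain *g* of 5, 10 or 20 LSAS points.

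- Shift in the difference = *p* × *g*
- Variance in the arm with excess uptake = 24² + *p*(1 − *p*)*g*²

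Excess on placebo, where the true difference becomes 10 − *pg*:

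| *p* | *g* | Difference | Power |
|---|---|---|---|
| 0.02 | 5 | 9.90 | 89.9% |
| 0.02 | 10 | 9.80 | 89.5% |
| 0.02 | 20 | 9.60 | 88.6% |
| 0.05 | 5 | 9.75 | 89.3% |
| 0.05 | 10 | 9.50 | 88.3% |
| 0.05 | 20 | 9.00 | 85.8% |

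Excess on active, where the true difference becomes 10 + *pg*: it runs from 10.1 (*p* = 0.02, *g* = 5) to 11.0 (*p* = 0.05, *g* = 20). If the drug has no effect, the true difference is *pg*, and the chance of passing the 1-sided 0.20 test is 20.6% at a shift of 0.1 and 26.5% at a shift of 1.0, instead of 20%.

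Equal uptake: the difference stays at 10 and only the variance rises. At *p* = 0.02, *g* = 5 the SD is 24.01 and power is 90.3%. At *p* = 0.05, *g* = 20 the SD is 24.39 and power is 89.7%.

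Relative to the SE, the shift is 0.1/4.66 = 2% to 1.0/4.66 = 21%.

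**The case against.** **The two terms may mean the same thing.** The only psychological treatments for SAD that the protocol names are cognitive and behavioral ones (Sections 1.2 and 3.2), so the sponsor may have intended one restriction throughout. This is possible, but the protocol uses two different wordings and defines neither. In a multi-center study, treating them as equal is left to each site.

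**Excess uptake on active is hard to explain.** The trial is double-blind with identical tablets, and chance imbalance is already covered by the test level. For the false-positive rate truly to rise, assignment itself would have to drive uptake, for example through side effects or guessed treatment. Non-responders on placebo seeking help is the more natural route, and that costs power only. This stands as a reason to regard the 20.6% to 26.5% range as a bound under assumption rather than an expectation.

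**The size is assumed throughout.** This is correct. The far end needs a 20-point gain, twice the drug effect the trial is sized for, from therapy with less than 12 weeks to act. At a 5-point gain the power loss is 1 percentage point or less.

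**Existing safeguards and limited effect of the fix.** CRF recording would make such use visible. The primary analysis stays ITT, and 1 to 3 deviations would be unlikely to trigger the per-protocol analysis in SAP Section 2.5.5. The amended rule would also still rest on an undefined term. All of this stands: the benefit is mainly deterrence, plus an entry in the deviation listing. It does not remove the inconsistency.

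**Conclusion.** The inconsistency is real: the entry rule bars specific psychotherapy for SAD, the on-study rules bar only cognitive behavioral therapy for SAD, and nothing else in either document covers the difference after Day 1. The consequence is probably small. Under assumed excess uptake of 2% to 5% and a gain of 5 to 20 points, the LSAS difference moves by 0.1 to 1.0 points, at most about a fifth of one standard error. The direction depends on which arm has the excess. Nothing in the documents indicates any uptake, benefit or imbalance, and the ITT comparison is valid as planned. This is a minor point, worth making because it is so cheap to correct.

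**What to change.** In Protocol Section 4.3, item 6, and the matching sentence in Section 8, replace the reference to cognitive behavioral therapy for SAD with: *any specific psychotherapy for SAD, including cognitive behavioral therapy*. This matches exclusion criterion 2 and leaves psychotherapy for comorbid MDD or GAD permitted. A breach would then be a protocol deviation and would be handled under SAP Section 4.5.

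The cost is one phrase in two sections. The restriction on subjects becomes slightly broader for at most 20 weeks (Protocol Section 3.1), extending a condition they already met at entry, and the deviation list may be slightly longer. No new CRF item, SAP table or change in sample size is needed.
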